##### 4.2.1 PRIMARY ENDPOINTS

Completion of the 2 visit protocol with acquisition of interpalpebral fissure height during resting open without the MLP, and with the MLP over 5 adjustable force levels.

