## 7 STUDY PROCEDURES AND SCHEDULE

### 7.1 STUDY PROCEDURES/EVALUATIONS

#### 7.1.1 STUDY SPECIFIC PROCEDURES

A cognitive pre-screening to guide the consent process will be administered as described in section 13.3.2. After consent, participants will have their acuity measured (refraction as needed), slit lamp with Nafl & NEI scale. Next, the MLP will be placed on the patient and video recordings made for 1 minute (comfort monitored with a 10-point scale during this period). Next, the effect of force adjustment via magnet rotation on lid position will be measured. The spectacle magnet will be rotated (settings labeled 1-4, counterbalanced), and videos recorded for another minute at each rotational increment. For video recording we will have 2 cameras: 1 straight on and the other angled up (to capture upper lid apposition to globe, Fig 5d&e). Recording will be done with a blue filter and NaFl to simultaneously document tear film. Additional NaFl will be added over the trial at the clinical staff discretion as needed. Once optimal rotational increment is found, a 20 minute trial at that setting will be performed with repeat of video recording with comfort and efficacy scale. Afterwards, the array will be removed and an array with the alternative polarization will be applied. We will then record for 1 min getting comfort and efficacy data and repeating the rotation experiment followed by another 20-minute trial. At the end of the study visit we will repeat visual acuity, slit lamp with Nafl & NEI cornea scale, and video recordings with comfort scale will be repeated. As this is a fitting and optimization process, it is possible that additional visits will be necessary in order to make modifications, but these will be optional.

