## 10 STATISTICAL CONSIDERATIONS

### 10.1 STATISTICAL AND ANALYTICAL PLANS

#### Statistical Analysis:

**Primary Outcome:** The effect of angular position on interpalpebral fissure during the resting open phase will be modeled using linear mixed-effects (multiple regression) models. The five angular (rotation) angles will be randomly mapped over the arbitrary labels of 1 to 5 to mask the participant and study staff and treated as categorical variables. Because repeated measurements will be performed on each eye and each participant might respond differently to each angular position, participant and angular position within participant-eye will be included as random effects. Demographic covariates, such as age and gender, will be evaluated to determine if they have a meaningful effect on interpalpebral fissure or comfort.

**Sample Size Calculation:** Data was originally not available to perform a sample size calculation for the mixed effects analysis. Instead we categorized the data for success versus failure defined as a clinically meaningful change of >1mm in interpalpebral fissure across the range of rotation forces. Based on this it was estimated that with 30 subjects we will have 80% power to show that the success rate significantly exceeds 50% with a one-sided alpha=0.025 exact binomial test of one proportion if the true success rate is 75% or greater. Therefore we originally aimed to enroll 30 subjects. Interim analysis was conducted after 11 subjects were enrolled and sample size calculation was adjusted down to 19 subjects.

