#### 10.4.2 ANALYSIS OF THE PRIMARY EFFICACY ENDPOINT(S)

Analyses will be performed by the study staff using statistical software (STATA 14 or similar). Primary outcome is the change in interpalpebral fissure with versus without MLP, and change in interpalpebral fissure across the 5 rotation angles.

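### Section 7.1.1 rotates the magnet over settings labelled 1-4 while the primary endpoint and analyses need five levels, and it names no comfort rating at each setting although comfort is modelled by angle

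*Combined protocol and SAP*

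**What the plan says.** Section 7.1.1 is the only description of how the rotation experiment is run; 7.3.2 and 7.3.3 simply refer back to it. After the device is placed there are "video recordings made for 1 minute (comfort monitored with a 10-point scale during this period"). The rotation step then follows: "The spectacle magnet will be rotated (settings labeled 1-4, counterbalanced), and videos recorded for another minute at each rotational increment". Once an optimum is found, "a 20 minute trial at that setting will be performed with repeat of video recording with comfort and efficacy scale". The array with the other polarization is then applied and the sequence is repeated. Video and comfort are recorded again at the end of the visit, at a setting that is not stated.

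The endpoint and the analyses count differently. Section 4.2.1, like the Protocol Summary, asks for fissure height without the device and "with the MLP over 5 adjustable force levels". Section 10.1 states: "The five angular (rotation) angles will be randomly mapped over the arbitrary labels of 1 to 5", in order to mask participants and staff. Section 10.4.2 takes as outcome the "change in interpalpebral fissure across the 5 rotation angles", and 10.4.3 uses five angles for the spontaneous blink. Section 10.4.3 also fits comfort with angular position as the fixed effect.

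In the schedule (7.3.7) the rotation rows are ticked at Visit 1 only, and the comfort scale has its own rows, none tied to a rotation setting.

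**The concern.** The endpoint is completion of the protocol with data at five force levels, and Section 3 makes continuation to a randomized trial depend on endpoints being met. If staff follow 7.1.1 as written and record four settings, no participant supplies the five levels.

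If staff instead count the placement recording as the fifth level, the five levels are not collected on equal terms. One is unlabelled in 7.1.1 and fixed in first place; the other four are labelled and counterbalanced. The primary model in 10.1 says that "participant and angular position within participant-eye will be included as random effects" but names no term for order.

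For comfort, the planned model needs ratings that vary by angle for reasons unrelated to the participant's response. The ratings named in 7.1.1 are taken either just after placement or at a setting chosen from that participant's own response.

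**Working it through.** The plan gives no figure for this point. Its one calculation, 80% power with 30 subjects, reproduces (exact binomial, success at 21 or more of 30: type I error 0.0214, power 0.803), but the number of levels is not an input to it.

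**Number of levels**

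| Place | Levels | Labels |
|---|---|---|
| Protocol Summary and 4.2.1 (endpoint) | 5 | none given |
| 7.1.1 (procedure) | 4, read literally | 1-4 |
| 10.1 (primary model) | 5 | 1 to 5, masked |
| 10.4.2 and 10.4.3 (outcomes) | 5 | none given |

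*Reading A, four settings.* Four of five levels are recorded. The angle effect has 4 − 1 = 3 degrees of freedom instead of 5 − 1 = 4, and 4×3/2 = 6 pairwise contrasts instead of 5×4/2 = 10. Over two arrays there are 2×4 = 8 angle recordings per eye instead of 2×5 = 10. For 19 participants, assuming one eye each, that is 152 instead of 190.

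*Reading B, placement plus four.* There are 1 + 4 = 5 recordings per array. Placement is first in every sequence, whereas under five-level counterbalancing each level would be first in 1/5 = 20%. Its order position is always 1; the other four average (2 + 3 + 4 + 5)/4 = 3.5. This mixes angle with order only if the starting angle is the same for all participants, and it matters only if fissure height changes over successive recordings. The documents give neither fact, so no size can be attached.

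The recording without the device cannot serve as the fifth level, because 4.2.1 lists it separately from the five levels with the device.

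**Comfort ratings named at Visit 1**

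- At placement of each array: named in 7.1.1; the angle is not stated.
- At each rotation setting: video only.
- With the 20-minute trial at the optimum: named for the first array. For the second array, 7.1.1 names the trial but no separate rating.
- At the end of the visit: named, setting not stated.

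At most two positions per array therefore have a rating that can be tied to a setting, against five in the model. The first is taken at about 1 minute of wear. The second is at about 1 + 4 + 20 = 25 minutes, if it follows the trial as the row order in 7.3.7 suggests and adjustment time is ignored. The optima may differ between participants, so more than two angles could appear in the pooled data. The problem is then less one of coverage than that angle is mixed with selection and wear time.

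**The case against.** The intended number is hardly in doubt: the endpoint and every analysis of angle on the fissure say five, and one parenthesis says 1-4. It may be a stale label, or shorthand for placement plus four increments. That is fair, and it makes this an inconsistency to reconcile rather than a flawed design. But 7.1.1 is the text staff follow, and nothing elsewhere reconciles it.

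A reader might infer that the primary angle effect is biased. The documents do not support that. It would require that placement is one of the five levels, that its angle is common to all participants, and that fissure height drifts between recordings. None of these is stated. If the random mapping in 10.1 is made separately for each participant, on which the text is silent, the starting angle need not be common. Nor can a possible order effect be judged against the "clinically meaningful change of >1mm in interpalpebral fissure across the range of rotation forces": that is a within-subject success criterion from the original sample size calculation, not a threshold for a mean contrast in the mixed model.

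A reader might also infer that comfort is not rated at each setting. The text only fails to name such ratings. Section 6.1 gives comfort as one purpose of adjusting the force, and 7.1.1 pairs video with the comfort scale at other recordings, so the omission may be loose drafting. The Visit 2 column header allows Visit 1 assessments to be repeated if the participant agrees, which could include the rotation experiment. However, the rotation rows are not ticked at Visit 2 and no settings are given for its ratings. Comfort is also secondary. These points lower confidence on comfort to moderate but do not supply the missing instruction.

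**Conclusion.** The point holds and should be fixed. The mismatch between settings 1-4 and five levels with labels 1 to 5 is certain on the text. Read literally, 7.1.1 provides four of five levels and cannot deliver the primary endpoint. On the placement-plus-four reading the count is right, but one level is always first and outside the labelled, counterbalanced set. An order effect on that level's contrast is then possible; its size is unknown and it depends on a common starting angle.

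The comfort point holds with moderate confidence, because it rests on what 7.1.1 and 7.3.7 leave unsaid. If only the named ratings are taken, they do not support a comfort-by-angle model.

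**What to change.** - Reconcile the number and labels of settings across 4.2.1, 7.1.1, 10.1 and 10.4.
- State whether the placement recording is one of the five levels. If it is, include it in the counterbalanced, masked order. If it is not, keep it outside the angle model.
- Record one comfort rating at each one-minute rotation setting, or report comfort descriptively instead of by angle.
- State the settings for the end-of-visit and Visit 2 ratings.
- For participants already enrolled (at least 11 of 19, since the interim analysis took place after 11), document which levels and ratings were obtained. Use per-setting ratings where they exist, without requiring a complete set. Do not treat placement or optimum-trial ratings as per-setting comfort data.

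The cost is a short amendment. If placement becomes a separate recording ahead of five labelled settings, there are 1 + 5 = 6 one-minute recordings per array instead of 1 + 4 = 5, or 12 instead of 10 over two arrays, plus one verbal rating per setting. Section 1 already assigns a staff member to the counterbalancing schemes. At most 19 − 11 = 8 participants can benefit from new data collection; what was not recorded for the others cannot be recovered.

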### 7.3 STUDY SCHEDULE

#### 7.3.1 SCREENING

**Pre-Screening:** In order to guide the consent/assent process, the approved study staff will administer a pre-consent cognitive screening using the Mini-Mental State Exam (MMSE). If score is 18-23 (maximum of 30) representing mild cognitive impairment (Tombaugh et al 1992), candidates will be asked return with a caregiver (if one is not present). If score is <18, they will not be eligible. **Screening/Study Intake:** Participants will have their acuity measured (refraction as needed), slit lamp with Nafl & NEI scale.

**Inclusion Criteria:** Presence of Blepharoptosis for at least one eye which occludes the visual axis in the resting state (no frontalis drive), moderate cognitive function or better defined as greater than or equal to 18 out of 30 on a pre-screening of the Mini-Mental State Exam, age 5 or older. **Exclusion Criteria:** Absence of ptosis which occludes the visual axis or presence of a corneal ulcer of any size. Age less than 5, Severe Cognitive impairment defined as MMSE score <18, behaviors consistent with delirium (combinations of disorientation, hallucinations, delusions, and incoherent speech), or lethargy. These individuals must be excluded since participation requires competent self-care, reliable responses and

cooperation during fitting of the device. Children need to be included because they represent an important target population (pediatric neuro-muscular conditions), and because facial structure and skin characteristics may result in a different response than adults

#### 7.3.2 Enrollment/Baseline

See 7.1.1 above

#### 7.3.3 Follow-up

See 7.1.1 above

---

#### 7.3.4 FINAL STUDY VISIT

At the final study visit a clinical decision will be made as to whether or not the MLP is recommended for continued use, and which version of the device was best. Because the MLP is not regulated by the FDA as a spectacle device (similar to low vision aids), and because there is no comparable alternative for non-surgical management, participant will be allowed to take the MLP and continue wearing it, and transferred to the clinical practice of the PI.

---

#### 7.3.5 EARLY TERMINATION VISIT

In the event a participant is terminated from the study due to an Adverse Event, the study PI will follow the participant for at least 30 days after termination to confirm the event has resolved or the patient is receiving appropriate treatment.

---

#### 7.3.7 SCHEDULE OF EVENTS TABLE

Procedures	VISIT 1 (ASSESSMENTS WILL BE REPEATED IF PARTICIPANT AGREES )	Visit 2 (1 week +/-2 days Visit 1 assessments will be repeated if participant agrees and the clinical staff will determine if this is clinically appropriate
Follow Up Phone Call		X
Visual Acuity (refraction if needed)	X	X
Slit Lamp Exam	X	X
NEI corneal staining scale	X	X
Baseline Video Recording	X	X
Eye Lid Prep	X	

Procedures	VISIT 1 (ASSESSMENTS WILL BE REPEATED IF PARTICIPANT AGREES)	Visit 2 (1 week +/- 2 days Visit 1 assessments will be repeated if participant agrees and the clinical staff will determine if this is clinically appropriate
Measurement of force to open the ptotic lid	X	
Polarity experiment, case 1 (apply lid magnet array)	X	
Video recording	X	X
10 point comfort and efficacy scale	X	X
spectacle magnet rotation experiment	X	
20 minute trial at optimum rotation	X	
Repeat Video Recording	X	
Repeat 10 point comfort and efficacy scale	X	
Polarity experiment, case 2 (apply lid magnet array)	X	
spectacle magnet rotation experiment	X	
20 minute trial at optimum rotation	X	
Video recording	X	
10 Point Comfort and Efficacy Scale		X
Repeat visual acuity	X	
Repeat Slit Lamp Exam	X	
Repeat NEI Nafl scale	X	
Clinical Decision		X

<Insert text>

## 7.5 CONCOMITANT MEDICATIONS, TREATMENTS, AND PROCEDURES

Oral and ophthalmic concomitant medications will be reviewed and recorded to confirm the patient does not have any systemic disease that would interfere with the study assessments and or data.

### 7.5.1 PRECAUTIONARY MEDICATIONS, TREATMENTS, AND PROCEDURES

none

## 7.6 PROHIBITED MEDICATIONS, TREATMENTS, AND PROCEDURES

Ophthalmic ointment or skin ointment applied near the eyes interferes with adhesion of the lid magnet and will need to be discontinued at least 1 day prior to the study. Patients may continue with artificial tears.

## 7.9 PARTICIPANT ACCESS TO STUDY AGENT AT STUDY CLOSURE

Because the MLP is not regulated by the FDA as a spectacle device (similar to low vision aids), and because there is no comparable alternative for non-surgical management, participants will be allowed to take the MLP and continue wearing it after completion of the study. MEEI has already approved provision of the MLP to non-research subject patients under the Humanitarian Devices rules.

# 8 ASSESSMENT OF SAFETY

## 8.1 SPECIFICATION OF SAFETY PARAMETERS

The safety of the study device will be evaluated at every visit following the enrollment visit and will be defined by the incidence of related adverse events. Specifically, we will evaluate:

- **Systemic safety:** Incidence and severity of systemic adverse events during the study (adverse events spontaneously reported or observed by the Research Assistant).
- **Ocular safety:** Incidence and severity of ocular adverse events during the study (ophthalmic examination, adverse events spontaneously reported).
- **SAFETY CUTOFFS: Should visual acuity decrease more than 2 lines, worsening of corneal rating of more than 1.5 points or other ocular surface ratings more than 2 points, and comfort rating lower than 5/10; study activities will cease for at least 1 week and an adverse event report to the IRB. Serious adverse events which will result in immediate dismissal from the study (and treatment) include: 1) development of a corneal epithelial defect or infiltrate without epithelial defect or 2) broken skin on the eyelid.**

### 8.1.1 DEFINITION OF ADVERSE EVENTS (AE)

Adverse Event (AE): Any untoward or unfavorable medical occurrence in a human subject, including any abnormal sign (for example, abnormal physical exam or laboratory finding), symptom, or disease, temporally associated with the subject's participation in the research, whether or not considered related to the subject's participation in the research.

---

#### 8.1.2 DEFINITION OF SERIOUS ADVERSE EVENTS (SAE)

**Serious Adverse Event (SAE):** Any event temporally associated with the subject's participation in research that meets any of the following criteria:

- Results in death
- Is life threatening
- Requires hospitalization/prolongation of hospitalization
- Results in congenital anomaly
- Results in persistent or significant disability/incapacity
- Required intervention to prevent permanent impairment/damage

---

#### 8.1.3 DEFINITION OF UNANTICIPATED PROBLEMS (UP)

Any incident, experience, or outcome (including data loss) that is unexpected (in terms of nature, severity, or frequency) given (a) the research procedures described in the protocol and the characteristics of the subject population being studied. Unanticipated problems may include protocol deviations that are not adverse events

### 8.2 CLASSIFICATION OF AN ADVERSE EVENT

The Investigator will promptly review documented adverse events and abnormal findings to determine 1) if the abnormal finding should be classified as an adverse event; 2) if there is a reasonable possibility that the adverse event was caused by the study device(s); and 3) if the adverse event meets the criteria for a serious adverse event.

---

#### 8.2.2 RELATIONSHIP TO STUDY DEVICE

If an adverse event or serious adverse event is recorded the study PI will determine the relationship to the study device.

### 8.3 TIME PERIOD AND FREQUENCY FOR EVENT ASSESSMENT AND FOLLOW-UP

Adverse events or abnormal findings thought to be associated with the study device will be followed until the event (or its sequel) or the abnormal finding resolves or stabilizes at a level acceptable to the Investigator. Events that have not resolved or stabilized will be followed for 30 days post study completion. Subjects will be encouraged to follow up with their physician for the treatment of any events beyond 30 days post study completion.

## 8.4 REPORTING PROCEDURES

### 8.4.1 ADVERSE EVENT REPORTING

All adverse events will be reviewed by the principal investigator within 24 hours of notification and reported to the Mass Eye and Ear IRB on the following schedule:

- Possibly, Probably, or Definitely Related Expected AE – Report to IRB on annual basis
- Possibly, Probably, or Definitely Related Expected Serious AE – Report to IRB on annual basis
- Possibly, Probably, or Definitely Related Unexpected AE – Report to IRB within 30 days of event
- Possibly, Probably, or Definitely Related Unanticipated Problem – Report to IRB within 7 days of event (24 hours for death of data loss)
- Possibly, Probably, or Definitely Related Unexpected Serious AE – Report to IRB within 7 days of event

### 8.4.2 SERIOUS ADVERSE EVENT REPORTING

Any adverse events that are serious, unexpected and related or possibly related to the study will be reported to the Mass Eye and Ear IRB within 7 calendar days from the time the PI becomes aware of the event.

Any unexpected and study-related death will be reported to the Mass Eye and Ear IRB within 24 hours of the PI's knowledge of the event by e-mail or telephone.

### 8.4.3 UNANTICIPATED PROBLEM REPORTING

All UAPs involving risks to subjects or others will be reported in writing to the Mass Eye and Ear IRB within 7 calendar days from the time the PI becomes aware of the event. If a UAP or an unexpected SAE results in a subject's death or was potentially life-threatening, the PI will notify the Mass Eye and Ear IRB through e-mail or phone within 24 hours from the time the event is identified. A follow-up report will be submitted if applicable, at a later date when more information is available. For UAPs that result in data loss the PI will notify the Mass Eye and Ear IRB through e-mail or phone within 24 hours from the time the UAP is identified.

## 10 STATISTICAL CONSIDERATIONS

### 10.1 STATISTICAL AND ANALYTICAL PLANS

#### Statistical Analysis:

**Primary Outcome:** The effect of angular position on interpalpebral fissure during the resting open phase will be modeled using linear mixed-effects (multiple regression) models. The five angular (rotation) angles will be randomly mapped over the arbitrary labels of 1 to 5 to mask the participant and study staff and treated as categorical variables. Because repeated measurements will be performed on each eye and each participant might respond differently to each angular position, participant and angular position within participant-eye will be included as random effects. Demographic covariates, such as age and gender, will be evaluated to determine if they have a meaningful effect on interpalpebral fissure or comfort.

**Sample Size Calculation:** Data was originally not available to perform a sample size calculation for the mixed effects analysis. Instead we categorized the data for success versus failure defined as a clinically meaningful change of >1mm in interpalpebral fissure across the range of rotation forces. Based on this it was estimated that with 30 subjects we will have 80% power to show that the success rate significantly exceeds 50% with a one-sided alpha=0.025 exact binomial test of one proportion if the true success rate is 75% or greater. Therefore we originally aimed to enroll 30 subjects. Interim analysis was conducted after 11 subjects were enrolled and sample size calculation was adjusted down to 19 subjects.

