#### 10.4.3 ANALYSIS OF THE SECONDARY ENDPOINT(S)

The effect of the five angular (rotation) angles on interpalpebral fissure during the spontaneous blink will be modeled using linear mixed-effects model, identical to that described for the primary outcome. Dependent variable will be the measured interpalpebral fissure during the 3 minima of each spontaneous blink event.

The effect of MLP compared to baseline without device will be modeled with another linear mixed effects model.

To model comfort level, we will treat the reported Likert-type data as interval data and use a linear mixed-effect model with angular position number as the fixed effect and participant and angular position number within participant-eye as random effects.

To statistically determine whether there are between-participant differences in response to angular position, we will employ profile analysis which is a multivariate statistical technique that uses multiple analyses of variance for repeated measures to test piecewise parallelism.

---

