#### 10.6.1 MASKING PROCEDURES

Only masked/blinded clinical staff will apply the lid magnets polarized either through thickness or through height (counterbalanced) to the study subjects.

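### The rotation experiment is run with two lid-array polarizations, but the angle, blink and comfort models have no polarity term, and the plan does not say which array's data enter either primary outcome

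*Combined protocol and SAP*

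**What the plan says.** **Procedures.** Section 7.1.1 describes a rotation experiment and a 20-minute trial with one lid array. Then: "Afterwards, the array will be removed and an array with the alternative polarization will be applied". Staff go on to "repeating the rotation experiment followed by another 20-minute trial". The schedule in Section 7.3.7 lists two polarity cases at Visit 1, each with its own rotation experiment. Under Section 10.6.1, masked staff "apply the lid magnets polarized either through thickness or through height (counterbalanced) to the study subjects". Polarity is therefore a deliberate second factor, crossed with angle within each participant.

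**Analysis.** In Section 10.1 the primary model has categorical angle as its effect, and "participant and angular position within participant-eye will be included as random effects". The only covariates mentioned are demographic. Section 10.4.3 uses the same model for the blink and describes the comfort model "with angular position number as the fixed effect and participant and angular position number within participant-eye as random effects". Of the device comparison it says only: "The effect of MLP compared to baseline without device will be modeled with another linear mixed effects model". Section 10.4.2 states: "Primary outcome is the change in interpalpebral fissure with versus without MLP", together with change across the five angles. It names no array for either part.

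Polarity is not mentioned anywhere in Sections 10.1 to 10.5. Sections 10.4.8 and 10.4.11 rule out subgroup and exploratory analyses, so they do not fill the gap.

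**The concern.** The trial takes the trouble to counterbalance a factor and then leaves it out of the analysis. If both arrays enter as written, the two recordings at one angle count as replicates, so any difference between arrays becomes residual error. The angle effect is then the average of two curves, which may differ. If only one array enters, the plan does not say which.

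The with-versus-without-MLP comparison is the most exposed, because the array on the device side is undefined. Section 7.3.4 has staff decide at the final visit which version of the device suited the participant best, and Section 10.4.7.2 foresees periodic preliminary analyses. An array rule settled after seeing the data would therefore be easy to fall into and hard for a reader to detect.

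**Working it through.** **1. The plan's own figure.** The one computed figure in Section 10.1 is 80% power with 30 subjects. It reproduces: the exact test needs 21 or more successes, with one-sided alpha 0.0214 and power 0.803 at 75%. It has no bearing on which array is analysed.

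**2. Size of the data set.** With 19 participants (Section 10.5), five angles (Section 10.1) and one eye each, the primary analysis has 19 x 5 = 95 records if one array enters and 190 if both do. The plan does not settle which.

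**3. Bias.** If every participant completes every angle with both arrays, polarity and period are balanced against angle. Leaving them out does not shift the averaged angle contrast.

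**4. Effect on the angle test.** The documents give no SDs, so these are assumptions: one value per recording, no Visit 2 repeats, recording SD 0.6 mm (variance 0.36), participant-by-array SD 0.3 mm (0.09), and participant-by-angle SD s = 0.3, 0.5 or 1.0 mm. Let D be the mean difference between arrays.

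- The correct error for angle is the participant-by-angle mean square on 18 x 4 = 72 df, with expectation 0.36 + 2s² = 0.54, 0.86 or 2.36.
- With polarity omitted, the residual has 72 + 18 + 4 + 1 = 95 df. Its expectation, for parallel curves, is 0.36 + 0.09 + D²/2 = 0.45, 0.575, 0.95 or 2.45 at D = 0, 0.5, 1 or 2 mm.
- A variance component cannot be negative. When the residual exceeds the participant-by-angle mean square, that component is set to zero and angle is tested against the pooled value (72 x first + 95 x second)/167.
- At s = 0.3 the pooled value is 0.56, 0.77 or 1.63 at D = 0.5, 1 or 2 mm, where 0.54 is correct.
- The crossing point is D = sqrt(2(0.36 + 2s² - 0.45)) = 0.42, 0.91 or 1.95 mm for the three values of s. At s = 1.0 and D = 2 the pooled value is 2.41 against 2.36, so almost nothing is lost.

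Simulation at s = 0.3 agrees. Type I error falls from 5% to 1% or below for D of 1 to 2 mm. With a 1.0 mm straight-line range on one array and 0.5 mm on the other, power falls from 98% to 94% (D = 1) or 44% (D = 2).

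**5. What the average conceals.** In that scenario the averaged range is (1.0 + 0.5)/2 = 0.75 mm, which describes neither array.

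**6. Choosing the array after the data.** Suppose the arrays are equal on average and each participant's better one is used. The excess over the average array is s_d/sqrt(pi), where s_d is the SD of one array's observed lift around the participant's own mean level. The setting on the device side is not stated, so two cases are shown.

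| Device value | s_d (mm) | Excess over average array (mm) | Real share, 0.09/s_d² | Real lift (mm) | Overstatement (mm) |
|---|---|---|---|---|---|
| Mean of five angles | sqrt(0.09 + 0.36/5) = 0.402 | 0.23 | 0.56 | 0.13 | 0.10 |
| One setting | sqrt(0.09 + 0.36) = 0.671 | 0.38 | 0.20 | 0.08 | 0.30 |

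**7. Precision per array.** The 95% half-width for an extreme-angle contrast is t(72) x sqrt(2(s² + 0.36/m)/19), with t = 1.993. For s = 0.3, 0.5 and 1.0 it is 0.34, 0.42 and 0.70 mm averaged over arrays (m = 2), and 0.43, 0.51 and 0.75 mm for one array (m = 1).

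**The case against.** **Pooling is the natural reading, and it is legitimate.** With one array and one value per angle, the angle-within-eye random effect could not be separated from residual error. The stated model thus makes most sense if both arrays, or other repeats, enter. This stands in part. The number of measurements per video is not given, so the reading is an inference, and the pooled model still lacks the factor.

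**The listed primary endpoint is feasibility.** Section 4.2.1 and the Protocol Summary define it as completing the visits and acquiring the measurements, which no array rule affects. Section 3 leaves a randomized comparison to a future application. This limits the consequence. It does not remove it, because Section 10.4.2 names fissure change as the primary outcome.

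**Polarity is not an objective, and the choice of version at the last visit is a clinical decision for one participant.** This stands. It is why per-array results should be descriptive, with no polarity test added.

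**The sizes are assumed.** This also stands. The documents contain no array-specific curves or SDs.

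**Conclusion.** The point holds as a should-fix. A counterbalanced design factor is absent from the three models whose terms are listed, and the array data behind both parts of the primary outcome are unspecified. On the assumed SDs, the omission makes the angle test clearly conservative only for array differences of about 1 mm or more, and only when participant-by-angle variation is modest. An array chosen after seeing the data would bias lift upward by the amounts in the table.

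A reader might infer more than the documents support:

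- That the averaged angle effect is biased. With complete data it is not.
- That every model excludes polarity. The MLP-versus-baseline model lists no terms, so there it is unspecified.
- That pooling would cost much of the power whatever the array difference. A large loss from averaging alone needs an array that does not respond to rotation, and nothing in the documents suggests one.
- That the sample size rests on a favourable array choice. The >1 mm success rule is used for sizing and is not the stated final analysis.
- That a polarity test would have the wrong error rate. The plan proposes no such test.
- That the better array will be picked. The plan does not say so; it only leaves room for it.

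**What to change.** In Sections 10.1, 10.4.2 and 10.4.3:

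- State that both arrays' data enter every model, including the with-versus-without-MLP comparison.
- Add fixed effects for polarity, angle by polarity, and array period (first or second applied). Add a random effect for array within participant-eye to those already stated. Recordings without the device have no polarity, so in that model code polarity within the device recordings and define lift as the mean over the two arrays minus no device.
- Name the array-averaged effect as the primary estimand for both angle and lift.
- Report the angle effect and the lift for each array with confidence intervals, as description.

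The cost is 1 + 4 + 1 = 6 fixed-effect degrees of freedom, one variance component, and the model wording and code. No new data or participants are needed. Because the averaged effect stays primary, the wider per-array intervals (29%, 19% and 7% wider at the three values of s) do not affect the main result. At the least, one sentence naming in advance the array data used for each outcome would remove the free choice, though naming a single array would discard half the recordings.
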